RESEARCH PROTOCOL

A RANDOMIZED CONTROLLED TRIAL TO COMPARE HYDROMORPHONE VS FENTANYL IN CHILDREN UNDERGOING TONSILLECTOMY SURGERY

[name]
Clinical Research Coordinator, Anesthesiology
[contact]

[name]
Professor, Otolaryngology
[contact]

[name]
CA3 Resident, Anesthesiology
[contact]

[name], PhD
Assistant Professor, Pediatric Anesthesiology
[contact]

Original Version: January 22, 2020

Revision: February 12, 2020

Revision: March 26, 2020

CONFIDENTIAL: This document is the intellectual property of [name] and [name], PhD. Acceptance of this document constitutes the agreement by the recipient that no unpublished information contained herein will be published or disclosed without prior written approval.

SYNOPSIS

Objective - To compare hydromorphone versus fentanyl for pain control following tonsillectomy or adenotonsillectomy surgery.

Study Period - 2 years

Number of Patients - 300 pediatric patients presenting for tonsillectomy or adenotonsillectomy at St. Louis Children's Hospital (SLCH)

Study Treatment - Hydromorphone vs fentanyl dosed per study design

Study Design - This is a randomized clinical trial with masked assessment, comparing recovery indices for patients receiving intermediate acting versus short acting opioid analgesia using hydromorphone or fentanyl as intraoperative analgesics. An otherwise standardized anesthetic and analgesic regimen will be utilized, consistent with routine care at SLCH. Patients will be randomized 1:1 in blocks of 4 within strata. Patients will be randomized to receive either hydromorphone or fentanyl throughout the perioperative period by opening a sealed protocol envelope.

Inclusion Criteria

1. Children ages 2 to 15 years old
2. Presenting for tonsillectomy or adenotonsillectomy surgery
3. American Society of Anesthesiologists Physical Status (ASAPS) Classification 1, 2 or 3
4. Provide Informed Consent / Assent (as appropriate)

Exclusion Criteria

1. Additional Concurrent surgeries, exclusive of myringotomy tubes, minor oral/nasal procedures (e.g. frenulectomy), and endoscopic procedures
2. Revision tonsillectomy or revision adenotonsillectomy surgery
3. Known pregnancy
4. Any condition which would make the participant, in the opinion of the investigator or the attending anesthesiologist caring for the patient, unsuitable for the study.

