There is currently not a standard of practice for pain management for tonsillectomy surgery at SLCH. Published guidelines recommend decreasing opioid doses in all patients with sleep apnea, for fear of respiratory depression, however they do not give recommendations regarding the use of short vs. intermediate acting opioids¹¹. The nurses in the SLCH PACU have subjectively noted a decreased need for opioid rescue analgesia when hydromorphone is administered intraoperatively as compared to fentanyl. Additionally, a recently completed prospective study of fentanyl versus hydromorphone for pain control in patients undergoing eye muscle surgery at SLCH suggests that hydromorphone results in lower pain scores and faster PACU recovery¹². There are limited data comparing different opioids in pediatric tonsillectomy surgery published in the literature. As far as we are aware, this will be the first randomized controlled trial comparing the intermediate acting opioid hydromorphone to the shorter acting opioid fentanyl for this patient population.

2.2. Rationale for the Study. Providing safe and effective pain control is important for these patients. Subjective observations indicate that hydromorphone may provide superior pain control as compared to fentanyl. This hypothesis has not been rigorously tested. We aim to ameliorate this deficit.

3. Study Objectives

3.1. Primary Aim. The **primary aim** of our study is to compare the need for rescue opioid analgesic medication between patients receiving fentanyl and hydromorphone following adenotonsillectomy surgery. We will also compare post-operative pain scores between the two groups, and the amount of opioid pain medications administered to patients postoperatively expressed in morphine equivalents. Patients will be randomized 1:1 in the operating room to receive either fentanyl or hydromorphone during the perioperative period. We hypothesize that compared to fentanyl, the use of hydromorphone will result in lower need for rescue opioid analgesic in post-surgical recovery.

3.2. Secondary Aims. The **secondary aims** of our study are to compare pain scores, the rates of post-operative respiratory complications, PONV, and length of PACU stay between patients administered fentanyl vs. hydromorphone. We hypothesize that there will be no differences between patients who receive fentanyl and those who receive hydromorphone.

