connected to the patient as per standard of care. Patients will be randomized to receive either hydromorphone or fentanyl in the operating room determined by opening a sealed protocol envelope. Administration and dosing of the randomized opioid to each case will be under the direction of the primary anesthesia team under the direction of the pediatric anesthesiologist caring for the child. In addition to the randomized opioid, patients will receive non-opioid analgesics and PONV prophylaxis as per routine care at SLCH. Blinding will be achieved using syringes prepared by SLCH investigational pharmacy.

4.7.4 Optional opioid Plasma Concentration Assessments. Approximately 3 mls of whole blood will be collected from patients at three time points: 1) within 10 minutes of administration of study drug, 2) within 10 minutes of PACU arrival, and 3) within 10 minutes of PACU discharge. Blood samples will be collected through an additional IV line placed in the surgical suite after anesthesia is given. Opioid (hydromorphone or fentanyl) blood levels will be measured using mass spectrometry. This type of analysis does not require *apriori* knowledge of the medication administered and will maintain the masking protocol. A Population Pharmacokinetic Analysis will be performed. The patient may decline to participate in the blood draw component of the study and remain in the study for data collection relating to the primary endpoint. Additionally, failed or missed blood draws in individual patients will not adversely affect the population analysis.

4.8. Treatment Regimen. Patients will receive a general anesthetic as per the standard of care at SLCH. Analgesia will include opioids and non-opioid adjuvants for pain in addition to anti-emetics per routine care at SLCH. Airway maintenance will be via an endotracheal tube supervised by the anesthesiologist responsible for the care of the patient in the operating room.

4.9. Method for Assigning Subjects to Treatment Groups. Patients will be randomized to either hydromorphone or fentanyl in the preoperative area prior to presenting to the operating room by investigational pharmacy staff. Randomization will be 1:1 in blocks of 4 within strata. Stratification will be done by age group (2-7, 8-12, and 13-15), and OSA diagnosed using sleep polysomnography within the last year.

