4.10. Preparation of the Study Drugs. Equi-analgesic dose tables poorly accommodate differences in rapid redistribution between drugs. Establishing a definitive therapeutic equivalence between hydromorphone and fentanyl for the patient population, type of stimulus, and duration of procedure is challenging *a priori*. Previous data gathered at SLCH and clinical expertise guide our dosing choices. Hydromorphone, when utilized as the sole opiate intraoperatively is dosed with median 10 ± 4 mcg/kg with 16 mcg/kg as the 80th percentile, and fentanyl is dosed with median 0.9 ± 0.5 mcg/kg, with 1.5 mcg/kg at the 80th percentile. We will use these current medians to guide our dosing. We will initiate medication dosing of patients with hydromorphone 10 mcg/kg, and fentanyl 1 mcg/kg. Conveniently, formulary preparation of hydromorphone is at 500 mcg / ml and fentanyl at 50 mcg/ml. Thus, blinding should be achievable as the same volume of medication (ml/kg) can be safely administered for each drug.

CONFIDENTIAL: This document is the intellectual property of [name] and [name], PhD. Acceptance of this document constitutes the agreement by the recipient that no unpublished information contained herein will be published or disclosed without prior written approval.

Regarding feasibility, we conducted an informal survey of attending anesthesiologists at SLCH. We had an approximately 50% response rate and all were willing to give these two drugs at the proposed doses in a blinded fashion.

5. Study Procedures

5.1. Screening for Eligibility. The patient's medical record will be screened for: age of child, type of surgical procedure planned, history of previous surgery, classification score for anesthesia, whether child is in custody of a legal caregiver, and ability to consent/assent to the study.

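### Sections 3.1 and 4.7.3 place randomization in the operating room, section 4.9 places it with the pharmacy beforehand, and section 5.5 separately conflicts with the masking

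*Combined protocol and SAP*

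**What the plan says.** Four places in the combined protocol and SAP describe allocation.

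- Section 4.7.3 (Administration): "Patients will be randomized to receive either hydromorphone or fentanyl in the operating room determined by opening a sealed protocol envelope".
- Section 3.1 (Primary Aim): "Patients will be randomized 1:1 in the operating room to receive either fentanyl or hydromorphone during the perioperative period".
- Section 4.9 (Method for Assigning Subjects to Treatment Groups) has patients randomized "in the preoperative area prior to presenting to the operating room by investigational pharmacy staff". It mentions no envelope.
- The Synopsis has the assigned opioid given "throughout the perioperative period by opening a sealed protocol envelope". It gives no place, no opener and no content for the envelope.

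Masking is described in three places. Section 4.7.3 says: "Blinding will be achieved using syringes prepared by SLCH investigational pharmacy". Section 4.10 concludes that "blinding should be achievable as the same volume of medication (ml/kg) can be safely administered for each drug" and reports an informal survey of attending anesthesiologists, about half of whom replied, in which "all were willing to give these two drugs at the proposed doses in a blinded fashion". Section 4.7.4 chooses an assay that needs no prior knowledge of the drug and so "will maintain the masking protocol".

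Section 5.5 (Medical Monitoring) has the PI watch all unblinded data as they accrue and pass the information to the anesthesiologists and surgeons.

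**The concern.** A site cannot follow both accounts. Under 4.9 the child is randomized before reaching the operating room, by the pharmacy. Under 3.1, and under 4.7.3 as it most naturally reads, the child is randomized after arriving there. Two things depend on which is meant.

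The first is masking. The primary outcome is the need for rescue opioid (3.1). Section 4.4 makes rescue available when more pain medication is needed, and no passage ties that decision to a pain score, so the outcome involves judgement. Sections 1.1 and 2.1 record that PACU nurses already believe hydromorphone patients need less rescue. If treating staff learned the assignment, rescue use could reflect expectation as well as the drug. Section 5.5 offers a second route to the same problem, independent of how allocation is done.

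The second is accounting for losses. Sections 4.6 and 10.2 replace children who withdraw, so that the group sizes are kept. Without one defined moment of randomization, it is unclear whether a child who drops out between the preoperative area and the operating room counts as lost after assignment or was never assigned.

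**Working it through.** The main question is textual. The allocation passages compare as follows.

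| Section | Where and when | Who | Means |
|---|---|---|---|
| Synopsis | not stated | not stated | sealed envelope |
| 3.1 | operating room | not stated | not stated |
| 4.7.3 | operating room (natural reading) | not stated | sealed envelope |
| 4.9 | preoperative area, before the operating room | investigational pharmacy staff | not stated |

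**Step 1: place and time.** 3.1 and 4.9 cannot both be true. In 4.7.3 the place could grammatically attach to receiving the drug instead of to the randomization. That would reconcile 4.7.3 with 4.9, but it does nothing for 3.1.

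**Step 2: means.** 4.9 names no physical device. Pharmacy staff opening an envelope in the preoperative area would satisfy both 4.9 and the Synopsis. The Synopsis is therefore incomplete and does not contradict 4.9.

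**Step 3: fit with the masked syringes.** The starting doses and formulary strengths in 4.10 give:

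- hydromorphone: 10 mcg/kg ÷ 500 mcg/ml = 0.02 ml/kg
- fentanyl: 1 mcg/kg ÷ 50 mcg/ml = 0.02 ml/kg

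The volumes agree, so equal-volume masked syringes fit the stated preparation. If the pharmacy fills syringes with the assigned drug, it must know the assignment when it fills them, and an envelope opened later in the operating room cannot determine it. The exception is a scheme in which the pharmacy supplies coded syringes of both drugs and the envelope selects a code. No passage describes one, and randomization would still be happening at the time and place that 4.9 excludes.

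**Step 4: what the envelope would reveal.** The documents do not say what it contains or who opens it. A code would preserve the masking. A drug name read by the dosing team would defeat the blinded administration that 4.10 expects.

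**Step 5: section 5.5 against 4.7.4 and 4.10.** The last two require that clinicians and assay staff work without knowing the drug. Section 5.5 places no limit on what is shared with anesthesiologists and surgeons: it does not restrict it to pooled data, to individual safety events, or to people outside the child's care.

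**The case against.** The firm clash is one phrase in an aims section against the section written to govern assignment. 4.7.3 has a reading that removes its conflict, and the envelope alone contradicts nothing. All of that is right, and it limits the point, but 3.1 still conflicts with 4.9, and the natural reading of 4.7.3 is the one a site is likely to follow.

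Pharmacy-prepared syringes also do not strictly require earlier assignment, because coded syringes would work. That stands as a possibility; the plan does not describe such a scheme.

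A reader might infer that the trial is unmasked or that concealment has failed. The documents do not support this. The stated design is masked assessment (Synopsis, 4.1), and the recovery nurse scores pain in the PACU (5.3). For an operating-room envelope to affect rescue use, it would have to name the drug and that knowledge would have to reach whoever decides on rescue. A route exists, since the attending accompanies the child to the PACU (4.4), but nothing shows it would be used.

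A reader might also want a false-positive rate. Any such figure would rest on an assumed shift in rescue use that no passage gives, and would say nothing about the size of this defect. Nor can a fixed count of affected assignments be given: 5.2 allows up to 360 consents to reach 300 patients, and withdrawals are replaced.

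Finally, 5.5 and the replacement rule would need attention even if allocation were described perfectly. That is fair. 5.5 is treated here as a separate conflict with the same masking, and replacement matters here only because it needs a defined starting point.

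**Conclusion.** The contradiction in place and time is real: 3.1, and 4.7.3 on its natural reading, against 4.9. The Synopsis adds an envelope of unstated purpose. Given pharmacy-prepared syringes and no described coded scheme, the account in 4.9 is the one that fits the masking plan. Unmasking through the envelope is a risk only if it names the drug. Section 5.5 is a distinct conflict: as written it lets information from unblinded data reach clinicians during a masked trial whose primary outcome depends on judgement. Whether by-arm information would in fact be passed on is not stated.

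The documents support no numerical size for either part. What can be said is that the allocation wording applies to every child assigned and that the repair is confined to text. It should be made, but it does not show that the design itself is unsound.

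**What to change.** Make the pharmacy route of 4.9 the only mechanism. Consent is already discussed in the preoperative area (5.2), so the order is workable. Section 4.9 could read:

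> Once consent, eligibility and stratum are confirmed, investigational pharmacy staff assign the next entry on the stratified list, which only the pharmacy holds, and release masked study-drug syringes labelled by study number. This assignment is the moment of randomization.

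Then:

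- Align 3.1, 4.7.3 and the Synopsis with it, removing randomization in the operating room.
- Either delete the envelope or state its role: opened only by the pharmacy, or holding only a code, or kept for emergency code-break with each opening logged.
- Report withdrawals, cancellations and replacements after allocation by arm.
- Amend 5.5 so that unblinded or by-arm information does not reach masked clinicians or PACU assessors.

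The cost is protocol wording; the pharmacy is already named both to randomize and to prepare the syringes. The downside is that a cancellation after pharmacy allocation becomes a post-randomization loss that has to be accounted for.

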5.2. Enrollment. The surgery schedule at SLCH is posted in advance therefore it is straightforward to determine daily if there are eligible subjects to approach for inclusion. The patient's medical history is available to screen for eligibility criteria prior to asking if they would be interested in participating. The day prior to the surgery, a nurse may contact the family to deliver preoperative instructions. At this time, the family may be told a study is being conducted and given details on possible participation. Additionally, the research team will identify potential patients on the day of surgery that may qualify for the study. A member of the research team will then approach the family in the private room in the surgical preoperative area to discuss the study and review the consent form. The study group will consist of 300 patients who are presenting for tonsillectomy surgery or tonsillectomy and adenoidectomy surgery. Enrollment completion will be achieved once consent for up to 360 patients is obtained, assuming a 20% drop-out rate from the study, with an end goal of 300 patients.

5.3. Schedule of Measurements. Consenting families will be evaluated with the YPAS-m scale prior to surgery. At the time consent is obtained, parents will also be asked to complete a brief demographic data form. Any preoperative sleep studies (also known as polysomnograms) that subjects had previously received will be reviewed. After surgery, the post-operative recovery nurse will evaluate the patient's pain using rFLACC scale on arrival to the Post Anesthesia Care Unit (PACU), and then every five minutes during the patient's stay. This is standard of care.

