5.5. Medical Monitoring. The PI will be monitoring all unblinded data as it is collected throughout the study and share the information with the anesthesiologists and the surgeons. In general, the Department of Anesthesiology has developed a specific set of Standard Operating Procedures (SOPs) for clinical research. All individuals working on study are required to read and be familiar with and compliant with the SOPs. The SOPs are in part developed from and are compliant with the Institutional Guidelines, including those for a) Interactions with the Washington University Human Subjects Review Committee, b) Informed Consent Development and Implementation, c) Subject Recruitment and Screening, d) Subject Management While on Study, e) Adverse Event Reporting. The potential risks of this study are attributable to the use of opioids in the perioperative period.

As already per routine care at SLCH, there will always be a non-study team attending anesthesiologist available both in the operating room and in the PACU to care for the patient in the event of any potential adverse event. This includes the availability of any resuscitation medications and/or equipment including but not limited to naloxone and emergent airway equipment.

5.6. Data Collection Procedures for Adverse Events. An adverse event would be evident as the study data on pain control, respiratory events, and PONV are collected as per routine standard of care.

5.7. Reporting of Adverse Events. Any adverse event will be reported to the IRB within 7 days as required. Any occurrences of serious adverse events or death will be reported within 24 hours.

6. Statistical Plan

6.1. Sample Size Determination and Sample Size Estimation. Sample size estimations were performed to determine the number of patients required to see a 50% reduction in the patients requiring rescue analgesia between the group receiving fentanyl and the

[figure not shown]
CONFIDENTIAL: This document is the intellectual property of [name] and [name], PhD. Acceptance of this document constitutes the agreement by the recipient that no unpublished information contained herein will be published or disclosed without prior written approval.

group receiving hydromorphone. Each estimation assumed achieving 80% Power, Alpha of 5%, 2 study groups at 1:1 ratio, and 20% attrition (equivalent by study group).

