Multiple power curves were calculated. As examples, assuming the proportion using rescue analgesics among patients in the fentanyl study group was 36% compared to a 50% reduction down to 18% for the hydromorphone group, a power analysis comparing independent proportions would require a total sample size of 228 participants. If 50% of the Fentanyl study group utilized rescue analgesics, detecting a 50% reduction down to 25% for the Hydromorphone group, a power analysis comparing independent proportions would require a total sample size of 139 participants (Fig. 1). We selected 300 patients based on an assumed proportion of 0.35 in the fentanyl group requiring rescue opioid analgesia and a goal of 50% reduction in patients requiring analgesia.

CONFIDENTIAL: This document is the intellectual property of [name] and [name], PhD. Acceptance of this document constitutes the agreement by the recipient that no unpublished information contained herein will be published or disclosed without prior written approval.

Figure 1: Sample size estimation curves. P2 = Fentanyl.

6.2. Analysis Plan. De-identified data will be entered into an excel spreadsheet and then SPSS will be used for data analysis. Demographic data will be summarized using descriptive statistics and the two groups will be examined for baseline differences. Descriptive statistics will include proportions, means, and standard deviation to determine statistically significant differences ($p<0.05$). If the differences at baseline are significant, confounders will be addressed using multivariate adjustment techniques. Alpha level 0.05 will be used.

7. Data Handling and Record Keeping

7.1. Confidentiality and Security. The consent forms and all questionnaires will be collected and stored in a locked file drawer in a locked office. Responses to questionnaires will be entered into a password protected computer. All study data will be entered into a database on a password protected computer. Only study team members will have access to the data. All reporting of data will be in the aggregate.

8. Risks, Study Monitoring and Administration

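### Section 5.2: 360 consents less the stated 20% drop-out leaves 288 patients, not the 300 end goal; power at the plan's assumed rates still exceeds 80%

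*Combined protocol and SAP*

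**What the plan says.** The synopsis gives one number: "300 pediatric patients presenting for tonsillectomy or adenotonsillectomy".

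Section 5.2 says "The study group will consist of 300 patients who are presenting for tonsillectomy surgery" and then explains how they will be obtained: "Enrollment completion will be achieved once consent for up to 360 patients is obtained, assuming a 20% drop-out rate from the study". The sentence goes on to the target: "assuming a 20% drop-out rate from the study, with an end goal of 300 patients". Here 300 is worded as the number left after drop-out.

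Section 6.1 sets the planning inputs: "Each estimation assumed achieving 80% Power, Alpha of 5%, 2 study groups at 1:1 ratio, and 20% attrition". It does not name the test or say whether alpha is two-sided. It gives two worked examples. For 36% v 18% the comparison "would require a total sample size of 228 participants", and for 50% v 25% it "would require a total sample size of 139 participants". It then says: "We selected 300 patients based on an assumed proportion of 0.35 in the fentanyl group requiring rescue opioid analgesia", with a 50% reduction as the goal.

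Sections 4.6 and 10.2 both say that a withdrawn child is replaced. Neither mentions the 360 consent limit.

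**The concern.** The three numbers in section 5.2 (360, 20%, 300) are tied together in one sentence, and any two of them contradict the third. The likely cause is a common slip: 20% was added to the target instead of dividing the target by 0.80.

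A reader needs to know how many analysed patients the plan expects, because that number fixes the power and the point at which consenting stops. A shortfall would matter if it took the trial below its 80% target. Section 6.1 adds to the uncertainty, because its text does not show the step from a 35% rate to 300 and because its estimates already contain a 20% allowance.

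**Working it through.** **Step 1. Section 5.2.** Inputs: 360 consents, 20% drop-out, goal 300 (all from 5.2).

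- Yield of 360 consents: 360 x (1 - 0.20) = 288. Gap to the goal: 300 - 288 = 12.
- Consents needed for 300: 300 / (1 - 0.20) = 375.
- Loss at which 360 gives 300: 1 - 300/360 = 16.7%.
- Source of 360: 300 x 1.2 = 360.

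This step needs no statistical assumption.

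**Step 2. Reproduce the section 6.1 examples.** Inputs: 80% power, alpha 5%, 1:1, 20% attrition (from 6.1). Two-sided alpha and a pooled test are my assumptions. With p the mean of p1 and p2, the number per arm is

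n = [1.960 x sqrt(2p(1-p)) + 0.842 x sqrt(p1(1-p1) + p2(1-p2))]^2 / (p1 - p2)^2,

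rounded up, doubled, and multiplied by 1.2 for attrition.

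| Rates | n per arm | Total | x 1.2 | Plan states |
|---|---|---|---|---|
| 36% v 18% | 94.31, so 95 | 190 | 228 | 228 |
| 50% v 25% | 57.67, so 58 | 116 | 139.2 | 139 |
| 35% v 17.5% | 98.05, so 99 | 198 | 237.6, about 238 | 300 selected |

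The first two rows match the plan. One-sided versions (180 and 111) and continuity-corrected versions (255 and 159) do not. An unpooled calculation divided by 0.8 comes close (230 and about 138).

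**Step 3. Other routes to 300 at 35% v 17.5%, 80% power.** Unpooled divided by 0.8 gives 240, pooled divided by 0.8 gives 248, and continuity-corrected versions give 264 to 275. None gives 300. The method in step 2 reaches 300 only at a fentanyl rate of about 29%.

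**Step 4. Power at 35% v 17.5%**, same test, two-sided 5%, with n analysed per arm:

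power = Phi{[0.175 x sqrt(n) - 1.960 x 0.6222] / 0.6098},

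where 0.6222 = sqrt(2 x 0.2625 x 0.7375) and 0.6098 = sqrt(0.35 x 0.65 + 0.175 x 0.825).

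| Analysed | What it represents | Power |
|---|---|---|
| 300 | Goal in 5.2 | 93.5% |
| 288 | 360 consents less 20% | 92.6% |
| 240 | 300 enrolled less 20% (300 x 0.80) | 87.4% |

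The gap of 12 patients costs 93.5 - 92.6 = 0.9 percentage points.

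**Step 5. Sensitivity to the fentanyl rate.** At 30% v 15%, power is 87.9% with 300 analysed, 86.6% with 288 and 79.8% with 240.

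**The case against.** **Replacement covers the gap.** Sections 4.6 and 10.2 replace withdrawn children, and 10.2 ties this to the required number, so 300 does not rest on the 20% figure alone. This stands in part: replacement could supply the 12. But nothing says that consents may exceed 360 for this purpose. If 360 is the ceiling for everyone, 20% loss still leaves 288.

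**300 may be a deliberate choice.** Section 6.1 says that several power curves were calculated and offers 228 and 139 only as examples. It does not call 300 the calculated minimum, and choosing more than the minimum is legitimate. Figure 1 is not shown here and may hold the explanation. The method in step 2 is also inferred from two numbers and is not stated in the plan. All of this stands, so the difference between about 238 and 300 is a question, not an error. A reader might note that 240 / 0.8 = 300 and infer that attrition was counted twice; the documents do not say so.

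**The meaning of 300 is clear.** Section 5.2 presents 300 as the number after drop-out, and no sentence in 6.1 says that the selected 300 is a number before attrition. This also stands in part. The figure of 240 analysed is an inference from the 20% allowance inside each 6.1 estimate, so it too is a query.

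**There is no practical consequence.** At the planned rates this is right, and it is why the point is minor.

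**Conclusion.** Section 5.2 is wrong as written: its own inputs give 288, not 300. This is plain arithmetic and depends on no choice of test. The cost is 12 analysed patients, or 0.9 points of power at 35% v 17.5%, and the 80% target is still met. The power figures assume a two-sided 5% pooled test, which the plan does not state.

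Two stronger conclusions are tempting and should not be drawn. One is that the trial is underpowered. At the plan's assumed rates it is not, with 300, 288 or even 240 analysed. The reassurance is limited to those rates, since 240 analysed at 30% v 15% would fall marginally below 80%. The other is that 300 in section 6.1 is a calculation error. The text does not show how 300 was reached, but it does not exclude a margin or an explanation in Figure 1.

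Severity: minor.

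**What to change.** Keep enrollment, the goal of 300 and the 360 limit unchanged. In section 5.2, state that 360 consents at 20% drop-out are expected to yield 288 patients. Give the power that follows: 92.6% at 35% v 17.5%, against 93.5% at 300, naming the test and the two-sided alpha assumed. Changing the drop-out assumption to 16.7% so that the sum closes is not advised, because it would fit an assumption to a total.

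Queries to the sponsor:

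- (a) How was 300 derived from a 35% fentanyl rate and a 50% reduction, when a calculation that reproduces 228 and 139 gives about 238? Is 300 a deliberate margin, or does Figure 1 explain it?
- (b) Is 300 in section 6.1 the number enrolled or the number analysed? If enrolled, 20% attrition leaves 240 analysed and 87.4% power at 35% v 17.5%.
- (c) Does replacement under sections 4.6 and 10.2 operate within the 360 consent limit?

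The cost is a few sentences of text, with no extra patients and no change to the design.
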